3.2 Exclusion Criteria

A patient will be excluded from the study if he or she meets **any** of the following criteria:

- 3.2.1 Received a prior CDK4/6 inhibitor.
- 3.2.2 Undergone major surgery within 14 days of the initial dose of study drug
- 3.2.3 Received another investigational agent (defined as any agent/device that has not received regulatory approval for any indication) within 14 days of the first dose of study drug for a nonmyelosuppressive agent, or 21 days of the first dose of study drug for a myelosuppressive agent.
- 3.2.4 Has any severe concurrent disease, infection, or comorbid condition that renders the patient inappropriate for enrollment in the opinion of the investigator.
- 3.2.5 Has an active bacterial infection (requiring IV antibiotics at the time of initiating study treatment), fungal infection, or detectable viral infection. Patients with known HIV infection are excluded given the potential for interactions between antiretroviral agents and abemaciclib, and the potential for increased risk of life-threatening infection with therapy that is myelosuppressive. Patients with known Hepatitis B or Hepatitis C infection are excluded only if there is evidence of active infection (detectable Hepatitis B surface antigen, detectable Hepatitis C RNA)
- 3.2.6 Documented brain metastases that are untreated, symptomatic, or require therapy to control symptoms. Participants with previously diagnosed brain metastases are eligible if they have completed treatment at least 7 days prior to trial registration, are neurologically stable, and have recovered from effects of radiotherapy or surgery.
 - Any corticosteroid use for brain metastases must have been discontinued without the subsequent appearance of symptoms for ≥ 2 weeks before the first study drug.
 - Treatment for brain metastases may have included whole brain radiotherapy, radiosurgery, or a combination as was deemed appropriate by the treating physician.
 - Patients who meet the above criteria and are clinically stable on anti-convulsant medication are eligible only if their anti-convulsant does not alter hepatic cytochrome P450 activity in a way that might interfere with metabolism of abemaciclib (see Appendix C).
- 3.2.7 Pregnant women are excluded from this study because of the potential for teratogenic effects.
- 3.2.8 Lactating women are excluding from the study.

- 3.2.9 Individuals with a history of a second malignancy are ineligible except for the following circumstances: individuals with a history of other malignancies are eligible if they have been disease-free for at least 5 years and are deemed by the investigator to be at low risk for recurrence of that malignancy. Individuals with the following cancers are eligible if they are diagnosed and have completed treatment within the past 5 years: cervical cancer in situ, and non-melanoma cancer of the skin. Patients with other cancers diagnosed within the past 5 years and felt to be at low risk of recurrence should be discussed with the principal investigator to determine eligibility.
- 3.2.10 Have received any live vaccination within 28 days of first dose of study drug.
- 3.2.11 Has a personal history of any of the following conditions: syncope of cardiovascular etiology, ventricular arrhythmia of pathological origin (including, but not limited to, ventricular tachycardia and ventricular fibrillation), or sudden cardiac arrest.

3.3 Inclusion of Women, Men, and Minorities

Both men and women of all races and ethnic groups are eligible for this trial.

4. REGISTRATION PROCEDURES

4.1 General Guidelines for DF/HCC Institutions

Institutions will register eligible participants in the Clinical Trials Management System (CTMS) OnCore. Registrations must occur prior to the initiation of protocol therapy. Any participant not registered to the protocol before protocol therapy begins will be considered ineligible and registration will be denied.

An investigator will confirm eligibility criteria and a member of the study team will complete the protocol-specific eligibility checklist.

Following registration, participants may begin protocol therapy. Issues that would cause treatment delays should be discussed with the overall Principal Investigator (PI). If a participant does not receive protocol therapy following registration, the participant's registration on the study must be canceled. Registration cancellations must be made in OnCore as soon as possible.

4.2 Registration Process for DF/HCC Institutions

DF/HCC Standard Operating Procedure for Human Subject Research Titled *Subject Protocol Registration* (SOP #: REGIST-101) must be followed.

5. TREATMENT PLAN

5.1 Treatment Regimen

Abemaciclib will be administered orally, twice daily on days 1 to 28 of a 28 day cycle as described in Table 5.1. Reported adverse events and potential risks are described in Section 7. Appropriate dose modifications are described in Section 6. No investigational or commercial agents or therapies other than those described below may be administered with the intent to treat the participant's malignancy.

TABLE 5.1 TREATMENT REGIMENS/DOSING SCHEDULE

Regimen	Period/Cycle	Dose Day
Abemaciclib	Treatment/28-day cycle	200 mg PO Q12H on Days 1-28
Abbreviations: PO=Orally		Q12H=every 12 (±2) hours.

The investigator or his/her designee is responsible for the following:

- explaining the correct use of the drug and planned duration of each individual's treatment to the patient/site personnel/legal representative,
- verifying that instructions are followed properly,
- maintaining accurate records of study drug dispensing and collection

For assessing compliance with treatment, the participant will be requested to maintain a medication diary of each dose of medication. The medication diary will be returned to clinic staff at the end of each cycle.

Patients will be instructed to contact the investigator as soon as possible if they have a complaint or problem with the study drug so that the situation can be assessed.

5.2 Pre-Treatment Criteria

On day 1 of cycle 1, blood will be drawn for complete blood count (CBC), liver function tests, urea, electrolytes, and creatinine. Results must be reviewed by the treating physician and meet the criteria below:

- Absolute neutrophil count $\geq 1500/\text{mm}^3$
- Platelets $\geq 100,000/\text{mm}^3$
- Hemoglobin ≥ 8 g/dL
- Total Bilirubin ≤ 1.5 x the upper limit of normal (ULN)
- Serum creatinine ≤ 1.5 mg/dL OR calculated GFR ≥ 60 mL/min
- Alanine aminotransferase (ALT) and aspartate aminotransferase (AST) ≤ 3 times the upper limit of normal. For patients with documented liver metastases, AST/ALT ≤ 5.0 times the upper limit of normal.

On day 1 of subsequent cycles, blood will be drawn for complete blood count (CBC), liver function tests, urea, electrolytes, and creatinine. Results must be reviewed by the treating

physician and meet the criteria below:

- Absolute neutrophil count $\geq 1000/\text{mm}^3$
- Platelets $\geq 100,000/\text{mm}^3$
- Total Bilirubin ≤ 1.5 x the upper limit of normal (ULN)
- Serum creatinine ≤ 1.5 mg/dL OR calculated GFR ≥ 60 mL/min
- Alanine aminotransferase (ALT) and aspartate aminotransferase (AST) ≤ 3 times the upper limit of normal. For patients with documented liver metastases, AST/ALT ≤ 5.0 times the upper limit of normal.

5.3 Agent Administration

- 5.3.1 Abemaciclib will be supplied as capsules for oral administration. The capsules should be stored at room temperature according to the range provided on the product label and not opened, crushed, or dissolved. Investigators should instruct patients to store the capsules in the original package and in a location inaccessible to children. Clinical study materials will be labeled according to country regulatory requirements.
- 5.3.2 Abemaciclib will be taken orally every 12 (± 2) hours on Days 1 through 28 of a 28-day cycle, for a total of 56 doses per cycle. Patients should not consume food beginning 1 hour before and ending 1 hour after taking abemaciclib. During all cycles, abemaciclib should be taken at approximately the same times each day. If a patient misses or vomits a dose, that dose should be omitted.
- 5.3.3 A patient may continue to receive study drug until she meets 1 or more of the specified reasons for discontinuation (as described in Section 5.5.)

5.4 General Concomitant Medication and Supportive Care Guidelines

With the exceptions provided in the sections below, no other chemotherapy, experimental medications, other anticancer therapy, immunotherapy, hormonal cancer therapy, surgery for cancer, or experimental medications will be permitted while patients are on study treatment. Radiation while on study treatment will be permitted after discussion with the PI.

The results from an in vitro human recombinant cytochrome P450 (CYP) phenotyping study indicate that oxidative metabolism of abemaciclib is primarily catalyzed by CYP3A4. However, the extent of oxidative metabolism responsible for the systemic clearance of abemaciclib in humans is unknown. Based on these in vitro findings, grapefruit juice as well as inducers (for example, phenytoin and carbamazepine) and strong inhibitors of CYP3A should be substituted or avoided if possible (Appendix C). If coadministration with a strong CYP3A inhibitor is unavoidable, reduce the abemaciclib dose to 100 mg twice daily or, in the case of ketoconazole, reduce the abemaciclib dose to 50 mg twice daily. In patients who have had a dose reduction to 100 mg twice daily due to adverse reactions, further reduce the abemaciclib dose to

50 mg twice daily. Avoid grapefruit or grapefruit juice. If a CYP3A inhibitor is discontinued, increase the abemaciclib dose (after 3-5 half-lives of the inhibitor) to the dose that was used before starting the inhibitor.

In vitro studies in primary cultures of human hepatocytes indicate that abemaciclib might inhibit the metabolism of CYP2B6 substrate drugs in vivo. Based on this finding, sensitive substrates of CYP2B6 such as bupropion and efavirenz should be substituted or avoided if possible.

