6. DOSING DELAYS/DOSE MODIFICATIONS

6.1 Dose Adjustments and Delays

Table 6.1 Toxicity Dose Adjustments and Delays for Abemaciclib

Toxicity Type	Toxicity Profile and Severity	Dose	
Hematologic Toxicity Sections 6.2 and 5.4.2	Requiring administration of growth factors, regardless of severity (Growth factors use permitted according to ASCO Guidelines)	Dose MUST be suspended for at least 48 hours after the last dose of blood cell growth factors was administered and until toxicity resolves to at least Grade 2.	Dose MUST be reduced by 1 dose level unless already performed for incidence of toxicity that lead to the use of growth factor.
Hematologic Toxicity Section 6.2	Grade 3	Dose MUST be suspended until toxicity resolves to at least Grade 2.	Dose MAY be reduced by 1 dose level - investigator's discretion.
Hematologic Toxicity Section 6.2	Recurrent Grade 3	Dose MUST be suspended until toxicity resolves to at least Grade 2.	Dose MUST be reduced by 1 dose level.
Hematologic Toxicity Section 6.2	Grade 4	Dose MUST be suspended until toxicity resolves to at least Grade 2.	Dose MUST be reduced by 1 dose level.
Non-hematologic Toxicity (except diarrhea and increased AST/ALT) Section 6.3	Persistent or recurrent Grade 2 that does not resolve with maximal supportive measures within 7 days to baseline or Grade 1	Dose MUST be suspended until toxicity resolves to either baseline or Grade 1.	Dose MUST be reduced by 1 dose level
Non-hematologic Toxicity (except diarrhea and increased AST/ALT) Section 6.3	Grade 3 or 4	Dose MUST be suspended until toxicity resolves to either baseline or	Dose MUST be reduced by 1 dose level.

		Grade 1.	
Diarrhea Sections 6.3.2 and 5.4.3	Grade 2	Dose MUST be suspended if toxicity does not resolve within 24 hours to \leq Grade 1.	Dose reduction is not required.
Diarrhea Sections 6.3.2 and 5.4.3	Persistent or recurrent Grade 2 that does not resolve with maximal supportive measures within 24 hours to at least Grade 1	Dose MUST be suspended until toxicity resolves to at least Grade 1.	Dose MUST be reduced by 1 dose level - investigator's discretion.
Diarrhea Sections 6.3.2 and 5.4.3	Diarrhea recurs despite maximal supportive measures after resuming same dose level after initial Grade 2 diarrhea	Dose MUST be suspended until toxicity resolves to at least Grade 1.	Dose MUST be reduced by 1 dose level.

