Diarrhea Sections 6.3.2 and 5.4.3	Requires hospitalization or Grade 3 or 4	Dose MUST be suspended until toxicity resolves to at least Grade 1.	Dose MUST be reduced by 1 dose level.
Hepatic Toxicity (AST and/or ALT) Section 6.3.4	Persistent or recurrent Grade 2 ($> 3.0-5.0 \times$ ULN) OR Grade 3 ($>5.0-20.0 \times$ ULN) that does not resolve with maximal supportive measures within 7 days to baseline or Grade 1	Dose MUST be suspended until toxicity resolves to baseline or Grade 1.	Dose MUST be reduced by 1 dose level.
Hepatic Toxicity (AST and/or ALT) Section 6.3.4	Grade 3 ($>5.0-20.0 \times$ ULN) AND Total Bilirubin $> 2.0 \times$ ULN, in the absence of cholestasis.	Discontinue Abemaciclib.	N/A
Hepatic Toxicity (AST and/or ALT) Section 6.3.4	Grade 4 ($>20.0 \times$ ULN)	Discontinue Abemaciclib.	N/A

Abbreviation: ASCO = American Society of Clinical Oncology.

Note: MAY = per the investigator's clinical judgment; SHOULD = not mandatory but highly recommended; MUST = mandatory.

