6.1.1 Abemaciclib Dose Adjustments

If a patient who, in the judgment of the investigator, is receiving clinical benefit from study therapy requires further dose reduction than is outlined in Table 6.1, then the investigator must discuss with the PI prior to any further dose reduction. For patients requiring dose reduction(s), re-escalation to a prior dose level is permitted only after consultation with the PI.

A cycle is defined as the planned treatment interval of 28 days plus any subsequent delay prior to start of the next cycle. A delay in the start of a cycle due to holidays, weekends, bad weather, or other unforeseen circumstances will be permitted up to 7 days and not counted as a protocol deviation. No more than 56 doses of abemaciclib should be dispensed for each 28-day cycle. Dose omissions are allowed within a cycle. If a patient requires omission of more than 25% of doses during a cycle for tolerability, then treatment may continue if the investigator determines

the patient is receiving clinical benefit.

Table 6.1.1 Dose Adjustments of Abemaciclib

Dose Adjustment	Oral Dose	Frequency
0	200 mg	Every 12 hours
1	150 mg	Every 12 hours
2	100 mg	Every 12 hours
3	50 mg	Every 12 hours

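### The Section 5.4 rule for stopping a CYP3A inhibitor names the pre-inhibitor dose as the target, which can undo a mandatory toxicity reduction made meanwhile and is not tied to the re-escalation clause in 6.1.1

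*Combined protocol and SAP*

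**What the plan says.** Section 5.4 asks that strong CYP3A inhibitors be substituted or avoided where possible, and then sets fixed doses for when they cannot be:

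- General rule: "If coadministration with a strong CYP3A inhibitor is unavoidable, reduce the abemaciclib dose to 100 mg twice daily".
- Ketoconazole: "in the case of ketoconazole, reduce the abemaciclib dose to 50 mg twice daily".
- Patients already reduced for toxicity: the target is the 50 mg level, given in the sentence that begins "In patients who have had a dose reduction to 100 mg twice daily due to adverse reactions, further reduce the abemaciclib dose to".
- When the inhibitor is discontinued: "increase the abemaciclib dose (after 3-5 half-lives of the inhibitor) to the dose that was used before starting the inhibitor".

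Section 6 governs dose changes for toxicity. For several events, among them Grade 4 and recurrent Grade 3 hematologic toxicity, Table 6.1 states "Dose MUST be reduced by 1 dose level", and its note defines the term: "MUST = mandatory". Table 6.1.1 gives the levels: 200, 150, 100 and 50 mg every 12 hours, with nothing below 50 mg. Section 6.1.1 adds: "For patients requiring dose reduction(s), re-escalation to a prior dose level is permitted only after consultation with the PI".

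**The concern.** The return rule in 5.4 is an instruction with one named target, the dose before the inhibitor. It does not ask what happened while the patient was on the inhibitor. If a toxicity forced a mandatory reduction in that interval, following 5.4 restores a dose that takes no account of it. Section 6.1.1 puts a condition on any return to a prior level, and 5.4 neither repeats that condition nor points to it.

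Nothing in the protocol says which section prevails. Table 6.1 cross-refers to 5.4.2 (growth factors) and 5.4.3 (diarrhea), but not to the inhibitor paragraph. The growth-factor rule in 5.4.2 shows that such coordination was possible, since it says what to do when a reduction for the same event has already been made. The inhibitor rule has no equivalent.

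What is at stake is patient safety after a severe toxicity, and a dosing instruction that two investigators could carry out differently in good faith. The primary analysis is not at issue: the two-stage decision rule counts responses and does not use dose.

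**Working it through.** There is no planned figure to reproduce. The check is to apply the rules as written, in order, from each starting level.

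**Inputs.** On-inhibitor doses and return rule: Section 5.4. Mandatory one-level reductions: Table 6.1. Levels: Table 6.1.1 (0 = 200 mg, 1 = 150 mg, 2 = 100 mg, 3 = 50 mg).

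**Step 1: strong inhibitor other than ketoconazole, with one mandatory toxicity reduction while on it.**

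| Dose before inhibitor | On inhibitor (5.4) | After one mandatory reduction (Table 6.1) | On stopping inhibitor (5.4) | Levels regained |
|---|---|---|---|---|
| 200 mg | 100 mg | 50 mg | 200 mg | 3 |
| 150 mg | 100 mg | 50 mg | 150 mg | 2 |
| 100 mg (reduced for adverse reactions) | 50 mg | no lower level listed | 100 mg | 1 |
| 50 mg (reached stepwise for adverse reactions) | 50 mg | no lower level listed | 50 mg | 0 |

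**Step 2: split the rise into its parts.** From 200 mg, the interaction adjustment was 200 to 100 mg, which is two levels (0 to 2). The toxicity reduction was 100 to 50 mg, one level (2 to 3). The return from 50 to 200 mg is 2 + 1 = 3 levels. The first two undo the interaction adjustment, which is the purpose of the rule. The remaining one undoes the mandatory toxicity reduction. From 150 mg the split is 1 + 1 = 2 levels, again with one belonging to toxicity. In nominal dose, 200/50 = 4 and 150/50 = 3.

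**Step 3: ketoconazole.** The on-inhibitor dose is already 50 mg, so a further one-level reduction has no place in Table 6.1.1. The sequence in Step 1 therefore needs a starting dose of 200 or 150 mg and a strong inhibitor other than ketoconazole. The return rule still names the pre-inhibitor dose in the ketoconazole case.

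**Step 4: compare with 6.1.1.** In both of the first two rows the patient has had a toxicity reduction and is returned to a prior level. That meets the terms of the re-escalation clause, which calls for PI consultation. Section 5.4 does not mention it.

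**Step 5: patient already at 50 mg.** Table 6.1 lowers the dose one level at a time, so a patient at 50 mg for toxicity has normally passed through 100 mg for adverse reactions. The sentence for such patients then applies and gives 50 mg, and the ketoconazole sentence also gives 50 mg. The inhibitor is added and the dose does not change. This gap lies in the starting rule, not in the return rule.

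**The case against.** The best defence is that 5.4 is silent on interim toxicity reductions and does not cancel them. It deals with reversing an interaction adjustment. Section 6.1.1 is a general condition that nothing in 5.4 waives, so an investigator can follow both by consulting the PI and then increasing the dose. A patient with an interim toxicity reduction is the one 6.1.1 covers most clearly.

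Part of this stands. It would be too strong to say that the protocol directs re-escalation without PI consultation; that is only an inference from 5.4 not repeating the condition. But adding the consultation does not change the target dose in 5.4, and neither section says how the toxicity reduction is to be carried forward. Reading 6.1.1 as limited to toxicity reductions does not help either, because the patient in question has had one.

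Three stronger readings are tempting and are not supported:

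- *That 5.4 raises a patient from 50 to 100 mg.* The sentence says to reduce, so it cannot sensibly direct an increase. The adverse-reaction sentence would normally govern and gives 50 mg.
- *That the four-fold rise measures the error.* Two of its three levels are the intended reversal. It is also a ratio of nominal doses with and without an inhibitor, not of exposures. Section 5.4 itself says that the contribution of oxidative metabolism to clearance in humans is unknown.
- *That dosing will differ between sites.* The documents show an ambiguity, not how any site resolves it.

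The reach is also narrow. The sequence needs an unavoidable strong inhibitor, a mandatory reduction on it, and withdrawal of the inhibitor while treatment continues, in a study of 38 patients. Known HIV infection and active fungal infection are excluded at entry, which removes some reasons for using the inhibitors in Appendix C. It is not remote, however. Sections 5.4.3 and 6.2 direct empiric antifungal therapy for persistent neutropenic fever (without naming an agent), Appendix C lists itraconazole and ketoconazole as strong inhibitors, and Section 2.2 reports 33% grade 3 neutropenia in the phase 1 study.

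At 50 mg, 6.1.1 already requires PI discussion before reducing further than Table 6.1 outlines, though 5.4 does not refer to it. This limb is therefore a gap, not a contradiction.

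**Conclusion.** The point holds in a limited form. Read literally, the return rule in 5.4 restores the pre-inhibitor dose whatever happened in between. For a patient starting at 200 or 150 mg with one mandatory reduction while on a strong inhibitor, one dose level of the resulting increase undoes that reduction. Section 5.4 also leaves open whether the PI consultation in 6.1.1 applies to the increase. The missing provision for a patient already at 50 mg is secondary, and the main conflict does not depend on it.

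This rests on taking 5.4 as an operative instruction and on stepwise toxicity reductions as Table 6.1 describes them. The number of patients affected cannot be derived from the documents and is probably small. The case for correcting the text is the safety consequence for an individual patient and the low cost, not any effect on the trial's conclusions.

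**What to change.** The sponsor should reconcile Section 5.4 with Table 6.1, Table 6.1.1 and the re-escalation clause in 6.1.1. The amended text should state:

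1. how a toxicity reduction made during inhibitor use carries over when the inhibitor stops;
2. whether the PI consultation in 6.1.1 applies to that increase, including when the only reduction was for the interaction;
3. what 5.4 means for a patient already at the 50 mg level who starts a strong inhibitor.

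A cross-reference between the inhibitor paragraph and Section 6 would help. The clinical rule is for the investigators to decide, and none is proposed here. The cost is a few sentences in a protocol amendment, with no extra data, visits or patients.

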5.4.1 Supportive Care

Patients should receive full supportive care to maximize quality of life. Patients will receive supportive care based on the judgment of the treating physician. If it is unclear whether a therapy should be regarded as supportive care, the investigator should consult the principal investigator (PI).

